## 3 OBJECTIVES AND ENDPOINTS

OBJECTIVES	ENDPOINTS	JUSTIFICATION FOR ENDPOINTS
Primary		

OBJECTIVES	ENDPOINTS	JUSTIFICATION FOR ENDPOINTS
Degree of Concordance Between Therapists' Feeding Therapy Recommendations	After reading a feeding case study, early intervention professionals will answer the question "Would you recommend feeding therapy?" with two choices: yes or no. Difference in agreement between early intervention professionals using the decision support tool and those not will be calculated and compared for cases A and B.	To determine whether using the tool, which helps identify feeding problem symptoms, changes decisions therapists make around recommending therapy for a child.
Degree of Concordance Between Therapists' Referral Recommendations	After reading a feeding case study, early intervention professionals will answer the question "Would you refer this family to any other providers/specialists for evaluation/treatment?" with two answer choices: yes or no. Difference in agreement between early intervention professionals using the decision support tool and those not will be calculated and compared for cases A and B.	To determine whether using the tool, which helps identify feeding problem symptoms by discipline with the explicit purpose of facilitating referrals, changes decisions therapists make around recommending referral to a specialist.
Degree of Concordance Between Therapists' Specific Specialist Referral Recommendations	After reading the feeding case study, early intervention professionals will answer the question "What other professionals would you refer this child to? Check all that apply." with the following choices: nutritionist/dietician, gastroenterologist, otolaryngologist (ENT), aerodigestive clinic, pulmonologist, occupational therapist, speech language pathologist, psychologist/social worker, applied behavior analyst (ABA), or allergist. Difference in agreement between early intervention professionals using the decision support tool and those not will be calculated and compared for cases A and B.	To determine whether the tool, which lists feeding problem symptoms by specialist discipline, changes the specialists a therapist refers to.
Secondary		

OBJECTIVES	ENDPOINTS	JUSTIFICATION FOR ENDPOINTS

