# 8 STUDY ASSESSMENTS AND PROCEDURES

## 8.1 EFFICACY ASSESSMENTS

To test intervention efficacy, the participant will be asked to answer a set of clinical questions after reading the case study. They will first do this without the intervention and then read another case study using the intervention. This will be administered through Qualtrics in survey form.

The questions include:

- Would you recommend feeding therapy to this child? Yes/No
  - If yes, "With what frequency would you recommend therapy?"
    - 2 times per week, 1 time per week, Less than one time per week
  - If yes, "What therapy target areas might you include for this child?" (select all that apply)

- Oral motor skills, sensory, behavioral, medication, modification of food/liquid, modification of equipment (seating, utensils, etc.), modification of environment (location, distractions, routine, etc), parent coaching, other (fill in)
- If yes, "What would be the recommended length of treatment for this child?"
  - Less than 6 months, 6-12 months, More than 12 months
- What diagnosis would you give this child?
- Would you refer this family to any other providers/specialists for evaluation/treatment? Yes/No
  - If yes, "What other professionals would you refer this child to? Check all that apply."
    - Nutritionist/dietician, gastroenterologist, otolaryngologist (ENT), aerodigestive clinic, pulmonologist, occupational therapist, speech language pathologist, psychologist/social worker, applied behavior analyst (ABA), allergist, multidisciplinary feeding team, other (list)

In addition to the clinical questions, the following questions will be asked in order for the participant to evaluate the tool:

- With a likert scale of completely agree, agree, neither agree nor disagree, disagree, completely disagree
  - The Clinical Feeding Guide meets my approval
  - The Clinical Feeding Guide is appealing to me
  - I like the Clinical Feeding Guide
  - I welcome the Clinical Feeding Guide
  - The Clinical Feeding Guide seems fitting
  - The Clinical Feeding Guide seems suitable
  - The Clinical Feeding Guide seems applicable
  - The Clinical Feeding Guide seems like a good match
  - The Clinical Feeding Guide seems implementable
  - The Clinical Feeding Guide seems possible
  - The Clinical Feeding Guide seems doable
  - The Clinical Feeding Guide seems easy to use
- If you could make changes to the CFG you would (check all that apply):

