### 9 STATISTICAL CONSIDERATIONS

#### 9.1 STATISTICAL HYPOTHESES

- Primary Efficacy Endpoint(s):
  - Degree of concordance between therapists’ feeding therapy recommendations
    - Null Hypothesis: There is no difference in therapists’ feeding therapy recommendations when using v. not using the tool

- Alternative Hypothesis: There is a difference in therapists' feeding therapy recommendations when using v. not using the tool
- Non-inferiority comparison
- Time period: After reading the case study
- Degree of concordance between therapists' referral recommendations
  - Null Hypothesis: There is no difference in therapists' referral recommendations when using v. not using the tool
  - Alternative Hypothesis: There is a difference in therapists' referral recommendations when using v. not using the tool
  - Non-inferiority comparison
  - Time period: After reading the case study
- Degree of concordance between therapists' specific specialist referral recommendations
  - Null Hypothesis: There is no difference in who the therapists recommend referral to when using v. not using the tool
  - Alternative Hypothesis: There is a difference in who the therapists recommend referral to when using v. not using the tool
  - Non-inferiority comparison
  - Time period: After reading the case study
- Secondary Efficacy Endpoint(s):
  - Degree of concordance between therapists' feeding therapy frequency recommendations
    - Null Hypothesis: There is no difference in therapists' feeding therapy frequency recommendations when using v. not using the tool
    - Alternative Hypothesis: There is a difference in therapists' feeding therapy frequency recommendations when using v. not using the tool
    - Non-inferiority comparison
    - Time period: After reading the case study
  - Degree of concordance between therapists' intervention target choices
    - Null Hypothesis: There is no difference in therapists' feeding therapy intervention target choices when using v. not using the tool
    - Alternative Hypothesis: There is a difference in therapists' feeding therapy intervention target choices when using v. not using the tool
    - Non-inferiority comparison
    - Time period: After reading the case study
  - Decision Support Tool Appropriateness
    - Null Hypothesis: The decision support tool is not appropriate.
    - Alternative Hypothesis: The decision support tool is appropriate.
    - Superiority
    - Time period: After using the tool

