### 9.4.2 ANALYSIS OF THE PRIMARY EFFICACY ENDPOINT(S)

For the following primary outcomes: degree of concordance between therapists' feeding therapy recommendations and degree of concordance between therapists' referral recommendations we have categorical data (2 groups – using tool and not using tool; 2 answers – yes or no). This is a repeated measure (therapists answer once for case A and once for case B). Each case will be analyzed separately. Due to the categorical data and small sample, reporting will be descriptive. Chi square tests will also be run if determined to meet the required assumptions. For chi-square tests, p value and effect size will be reported. These will be independent and therefore, adjustment for multiple comparisons will not be pursued.

For the third primary endpoint, degree of concordance between therapists' specific specialist referral recommendations, descriptive statistics will be used due to the multiple categories, small counts, and small sample size. The percentage of therapists recommending a particular provider will be compared among therapists using and not using the tool.

Across all analyses, missing data will be reported but not corrected for due to the small sample size. Participants who did not complete all survey items will not be included in analysis. Adjustment for multiple comparisons is considered unnecessary due to the small sample size and minimal use of inferential statistics.

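### The third primary endpoint has a null and an alternative hypothesis, but the plan gives only side-by-side percentages, with no interval or test to assess them

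*Combined protocol and SAP*

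**What the plan says.** Section 9.1 gives the third primary endpoint a formal pair: "Null Hypothesis: There is no difference in who the therapists recommend referral to when using v. not using the tool" and "Alternative Hypothesis: There is a difference in who the therapists recommend referral to when using v. not using the tool". It labels the comparison "Non-inferiority comparison" and gives no margin.

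Section 9.4.2 then limits the analysis: "descriptive statistics will be used due to the multiple categories, small counts, and small sample size". The only quantity named there is a percentage per provider: "The percentage of therapists recommending a particular provider will be compared among therapists using and not using the tool". Section 3 promises a difference in agreement for each case but names no agreement index and no measure of uncertainty.

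The other two primary endpoints, and therapy frequency in section 9.4.3, get a chi-square test with p value and effect size if the assumptions hold. The third primary endpoint has no counterpart. Section 9.4.2 also rules out adjustment for multiple comparisons. Section 9.2 calls the study a pilot and bases its size on funding and balance.

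The option list differs between sections. The endpoint definition in section 3 ends with "psychologist/social worker, applied behavior analyst (ABA), or allergist", which makes 10 options. The survey in section 8.1 continues: "applied behavior analyst (ABA), allergist, multidisciplinary feeding team, other (list"), which makes 12.

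**The concern.** A stated hypothesis needs an analysis that could count for or against it, and for this endpoint none is planned. The tool is a referral checklist organised by specialist area, so this endpoint bears closely on what the tool is meant to change.

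The reasons given (many categories, small counts, small sample) argue against an asymptotic chi-square. They do not argue against showing the uncertainty of each difference. A table of 10 to 12 specialists in two cases, without intervals, gives the reader 20 to 24 differences and no means of telling which are larger than chance would produce. At stake is whether the results can be interpreted at all, and whether section 9.1 claims more than section 9.4.2 can deliver.

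**Working it through.** There is no power calculation to reproduce. The target of 56 is 2 × (14 + 14), which is arithmetically correct and is said to rest on funding and balance.

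**Inputs from the documents**
- Within each case, 28 therapists answer with the tool and 28 without (sections 1.2, 4.1 and 6.3).
- There are 10 options (section 3) or 12 (section 8.1). Over two cases this makes 20 to 24 comparisons.

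**Assumptions**
- Referral rates: the documents give none, so a range is shown.
- A gap of 20 points is used as an illustrative threshold; it is not in the plan. Since 0.20 × 28 = 5.6, it means a difference of at least 6 therapists.

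**Step 1: one specialist, no tool effect.** With X and Y independent Binomial(28, p), q(p) = P(|X − Y| ≥ 6), computed exactly:
- p = 10%: 1.5%
- p = 20%: 6.5%
- p = 30%: 10.8%
- p = 50%: 14.1%

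**Step 2: at least one such gap among 12 independent options in one case.** P = 1 − Π(1 − q_j). If every rate is 10%, 1 − (1 − 0.0146)^12 = 0.162. If every rate is 50%, 1 − (1 − 0.1409)^12 = 0.838. The last column is 1 − (1 − P)², which treats the cases as independent although the same therapists answer both.

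| Assumed rates, 12 options | One case | Both cases |
|---|---|---|
| All 10% | 16% | 30% |
| Mostly rare: five at 5%, three at 10%, two at 20%, one at 50%, one at 60% | 38% | 62% |
| Evenly spread 5% to 40% | 60% | 84% |
| Evenly spread 10% to 60% | 73% | 93% |
| All 50% | 84% | 97% |

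With the 10-option list and rates spread over 5% to 40%, the figures are 53% and 78%.

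**Step 3: correlation between options.** A latent-normal simulation (4,000 trials per setting, correlation 0.3 or 0.5, all rates 30% or 50%) gave 66% to 80% for 12 options in one case. Under independence the same rates give 75% and 84%. Correlation lowers the figure without removing the issue.

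**Step 4: precision of one difference.** The Wald 95% half-width is 1.96 × √(2p(1 − p)/28).
- p = 10%: 1.96 × √(0.18/28) = 15.7 points
- p = 20%: 21.0 points
- p = 30%: 24.0 points
- p = 50%: 1.96 × √(0.50/28) = 26.2 points

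**Step 5: would a test per specialist be better?** At an assumed 0.05 each, the nominal familywise error over 12 independent tests is 1 − 0.95^12 = 46%, and over 24 it is 1 − 0.95^24 = 71%. With Bonferroni over 12, power to detect 30% v 60% falls from 62% to 26%. Intervals, or one global test per case, suit this sample size better.

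**The case against.** The strongest reply is that section 9.4.2 openly calls this analysis descriptive, gives its reasons, and belongs to a funding-limited pilot. That largely stands: a descriptive analysis is defensible at 28 v 28. It does not explain why section 9.1 keeps a hypothesis that the analysis cannot address, and a descriptive report can still carry intervals.

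The chance figures also depend on assumed rates and on a threshold that is not the plan's. The plan's own expectation of small counts points towards the lower rows of rates, where the figure for one case is 16% or 38%. This is fair, and it is why the whole range is shown.

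A reader might infer that chance differences will be read as tool effects, or that some specialist will almost always appear changed. The documents support neither. No rule in the plan turns a gap into a tool effect, and a gap is more likely than not only under the higher assumed rates.

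A reader might also infer that leaving out a permutation test is an error. It is not; such a test is an option. Section 6.3 assigns by alternating order of entry within discipline, so a permutation p-value would rest on exchangeability within discipline and not on actual randomisation.

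**Conclusion.** The concern holds as a mismatch between sections 9.1 and 9.4.2, together with the absence of any planned measure of uncertainty for a primary endpoint. As written, the hypothesis cannot be assessed and readers cannot judge chance variation.

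The risk of mistaking noise for an effect ranges from small to large. With no tool effect, the chance of at least one 20-point gap among 12 options in one case is 16% to 84% over the assumed rates, with independent options and full groups of 28. One difference carries a 95% half-width of about 16 to 26 points. Misreading such gaps is a possible consequence of the plan, not something that it states.

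**What to change.** - **Section 9.4.2:** keep the percentages. For each specialist and each case, add the tool minus no-tool risk difference with a 95% CI by a small-sample method such as Newcombe. State that the intervals are unadjusted across the 20 to 24 comparisons and do not by themselves establish a tool effect.
- **Section 9.1:** replace the null and alternative hypotheses for this endpoint with a descriptive estimation aim. The non-inferiority label, which has no margin, should go with them.
- **If the hypothesis is kept instead:** pre-specify one global permutation test per case, with tool labels shuffled within discipline and the maximum standardised difference over specialists as the statistic. State that it assumes exchangeability, because assignment alternates by entry order.
- **Sections 3 and 8.1:** reconcile the 10-option and 12-option lists.

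The cost is a few sentences of plan text and, for the test, a few lines of code. No more participants or survey items are needed. The downside is wide intervals and modest power for any single specialist, which the intervals make visible.

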## 5.5 STRATEGIES FOR RECRUITMENT AND RETENTION

The target sample size is 56 participants with 28 SLPs and 28 OTs. We anticipate one site will be used – UNC Chapel Hill; although the study will be completed virtually by participants. Target enrollment will not be stratified for age, gender, or race/ethnicity for this pilot study, but future studies will control for these variables. Because participants are expected to be practicing in early intervention, participants will be recruited from private practices (which contract with early intervention) and from the early intervention system in North Carolina. Participants will be recruited through web search, the Child Developmental Services Agency, and word of mouth. Potential participants will be emailed through these groups and will be directed to an interest survey where they will complete a screening. If eligible and interested, they will provide their name and email. In the order of entry, the PI will email them a link to the survey.

Because the fields of occupational therapy and speech language pathology are majority female, specific female recruitment is not necessary. For this pilot study, participants will not be specifically selected for race/ethnicity, but this will be pursued in future, larger studies.

Participants who complete the full survey will receive a \$25 gift card as an incentive.

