  - Make it shorter, make it longer/more comprehensive, change the format, add items, remove items, I wouldn't make any changes, I wouldn't use it
- Please list 1-2 strengths of the CFG
- Please list 1-2 changes you would make to the CFG to make it more useful for clinical practice
- I would use the CFG in clinical practice (5pt likert scale from strongly agree to strongly disagree)
  - If Strongly, somewhat, or neither agree/disagree is selected: "Please describe why you would use the CFG in clinical practice"
  - If somewhat disagree, strongly disagree or neither agree/disagree is selected: "Please describe why you would not use the CFG in clinical practice"

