## 9.2 SAMPLE SIZE DETERMINATION

This is a pilot study. Sample size was selected based on available funding and to achieve equal numbers in each group (group 1: case A then case B; group 2: case B then case A) as well as equal numbers of SLPs and OTs per group (group 1: 14 SLP, 14 OT. Group 2: 14 SLP, 14 OT).

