## 9.3 POPULATIONS FOR ANALYSES

All participants who completed the full survey will have their data included in analysis. Partial survey responses will not be included.

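### Leaving any one survey item blank removes a therapist from every primary and secondary endpoint analysis, even when the primary answers are complete

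*Combined protocol and SAP*

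**What the plan says.** Section 9.3 defines a single analysis population, those who completed the full survey, and adds: "Partial survey responses will not be included". Sections 9.4.2 (primary endpoints) and 9.4.3 (secondary endpoints) each repeat the rule in a paragraph that applies across all analyses: "Participants who did not complete all survey items will not be included in analysis". No item is exempted, and no available-case or sensitivity set is described. The preceding sentence in both sections says that "missing data will be reported but not corrected for due to the small sample size".

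Section 8.1 lists the survey content. The clinical questions are asked for each case. The document then says "In addition to the clinical questions, the following questions will be asked in order for the participant to evaluate the tool". Among the latter are "Please list 1-2 strengths of the CFG" and "Please list 1-2 changes you would make to the CFG to make it more useful for clinical practice".

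On size, section 5.5 states "The target sample size is 56 participants with 28 SLPs and 28 OTs", and section 9.2 asks for "equal numbers of SLPs and OTs per group (group 1: 14 SLP, 14 OT. Group 2: 14 SLP, 14 OT").

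**The concern.** The three primary endpoints in section 3 need little from each therapist: a yes/no on feeding therapy, a yes/no on referral and, after a yes to referral, a check-all list of specialists, for each case. The completeness rule makes use of those answers depend on every other item in the survey, several of which feed no primary or secondary endpoint.

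Two things are at stake. The first is precision: observed, valid primary answers are deleted from a study that is already small and analyses each case separately. The second is selection. The tool questions come after the therapist has used the tool, so being kept in the analysis depends partly on behaviour after exposure.

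The wording is also unclear in two places. Missing data are to be reported, yet a set stripped of every blank contains none. And several items appear only after a yes, but the plan does not say that an item never shown does not count as incomplete.

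**Working it through.** **Planned size.** 4 cells x 14 = 56, which reproduces the stated figure. There is no power calculation to check, because section 9.2 bases the size on funding and balance.

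**Item count from section 8.1, demographics excluded, for a therapist who answers yes to therapy and referral in both cases.**
- Per case: therapy, frequency, targets, treatment length, diagnosis, referral, specialists = 7. Two cases = 14.
- Tool: 12 ratings, change checklist, strengths, changes, intended use, reason for use or non-use = 17.
- Total: 14 + 17 = 31.

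**Split by use.**
- Primary endpoints: 3 per case x 2 = 6.
- Secondary endpoints: frequency and targets, 2 per case x 2 = 4, plus 12 ratings = 16.
- No endpoint: diagnosis and treatment length, 2 per case x 2 = 4, plus 5 tool questions = 9.
- Check: 6 + 16 + 9 = 31.

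**Illustrative loss.** The documents give no skip rate, so q, the chance that a therapist skips any given item, is assumed, with skips independent. The share dropped under the written rule is 1 - (1 - q)^31. The expected number kept is 56 x (1 - q)^31 under the written rule, against 56 x (1 - q)^6 if only the six primary items had to be answered.

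| Assumed q | Share dropped | Kept, written rule | Kept, six primary items | Complete primary answers discarded |
|---|---|---|---|---|
| 0.25% | 7.5% | 51.8 | 55.2 | 3.3 |
| 0.5% | 14.4% | 47.9 | 54.3 | 6.4 |
| 1% | 26.8% | 41.0 | 52.7 | 11.7 |
| 2% | 46.5% | 29.9 | 49.6 | 19.7 |

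**Effect on precision.** The standard error of a percentage scales with 1/sqrt(n). Against the six-item requirement, the written rule widens it by sqrt(54.3/47.9) = 1.06 at q = 0.5% and by sqrt(52.7/41.0) = 1.13 at q = 1%.

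**Only the three open-text tool items skipped.** The share dropped is 1 - (1 - q)^3. At 2%, 5% and 10% per item the written rule keeps 52.7, 48.0 and 40.8 of 56. An endpoint-specific rule keeps all 56.

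**Sensitivity to independence.** If the same few therapists skip everything, the share dropped falls to q itself: at 1%, 56 x 0.01 = 0.56 of a person. Those therapists would have no primary answers to save. The independent figures are therefore not a forecast.

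**The case against.** The strongest reply is that the loss may be small. The survey runs in Qualtrics. If every item forces a response, isolated blanks cannot occur and only break-offs remain. Section 5.5 pays the gift card on full completion, section 7.3 requires a reminder and at least two emails before someone is deemed lost, and section 7.2 provides for replacing withdrawn or discontinued participants. This is a pilot reported descriptively, so no power claim is undermined. Sections 4.4 and 6.4 speak only of completing the survey, so the authors may have had abandoned surveys in mind, not single blanks.

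Much of this stands as a limit on size. It does not remove the point. The documents do not state a forced-response setting. Section 7.1 lets participants stop at any time, so someone who stops among the tool questions after answering both cases is discarded even if responses are forced. Replacement does not mention item-skippers, does not recover their answers and does not remove selection. Small size is a reason to keep observed answers.

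A reader might go further and infer that the rule inflates the acceptability, appropriateness and feasibility scores. The documents do not support that: nothing links skipping to a poor opinion of the tool, and a therapist who leaves the ratings blank has no score under any rule. Nor do they support a claim that the rule tilts the tool comparison in a known direction. Every therapist uses the tool on the second case, so the filter acts on both groups.

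**Conclusion.** The point holds. As written, the plan discards complete primary answers because of blanks elsewhere, including in nine items that feed no endpoint, and it makes inclusion depend on behaviour after exposure to the tool. The direction and size of any bias are unknown.

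The 14% to 27% figure rests on assumed skip rates of 0.5% to 1%, independence across items and the longest path through the survey. It is an illustration and would be lower with clustered skips or forced responses.

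Three stronger readings should be set aside. Loss of the planned 14 per discipline per group is possible but not certain, since replacement may restore numbers in some cases. Exclusion of everyone who answers no, because the follow-up items stay blank, is a literal reading that the authors presumably did not intend; it calls for a definition. And the rule reaches the primary and secondary endpoint analyses, not clearly everything: the monitoring of concerning responses in section 9.4.4 is not limited to completers.

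The change is worth making before analysis, because the wording is plain and the remedy is cheap.

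**What to change.** Revise sections 9.3, 9.4.2 and 9.4.3 to define the analysis set by endpoint and by case:

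- For each case, include every therapist who answered that endpoint's question for that case, whatever other items or the other case show.
- Do not require answers for both cases. The cases are analysed separately, and the specialist, frequency and target items appear only after a yes. A both-case rule would drop therapists whose answer changes between cases, a change that the tool itself may produce.
- Define completeness as items actually presented. A no to therapy or to referral is a valid response. For specialist percentages, a no to referral counts as no specialist selected. Summarise frequency and targets among those who recommended therapy for that case.
- For each rating scale, include therapists who answered all 4 of its items.
- Report n for each endpoint and case, and keep the full-completer set as a sensitivity analysis.
- State whether Qualtrics forces responses, and whether answers already given by someone who stops and is replaced are kept.

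The cost is SAP wording. The downside is that n may differ slightly between endpoints and cases.
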